### **6.3.2. Last Observation Carried Forward (LOCF)**

Continuous efficacy and health outcomes variables will be summarized using a last observation carried forward (LOCF) method. For patients discontinuing study treatment for any reason, the last non-missing post-baseline observation before the missing data will be carried forward to the corresponding time point for evaluation. Enrolled patients without at least 1 post-baseline observation will not be included for evaluation.

## **6.4. Multicenter Studies**

This study will be conducted in multiple investigators at multiple sites. However, since all sites will have small numbers of subjects, center differences will not be explored.

## **6.5. Multiple Comparisons/Multiplicity**

No statistical multiple comparisons will be made in this single arm study with very small sample size.

## **6.6. Use of an “Efficacy Subset” of Patients**

An efficacy subset will not be used in this study because of very small sample size.

## **6.7. Patient Disposition**

The following patient disposition summaries will be provided for patients with GPP and EP separately and total:

- Number of patients:
  - failed in screening, by primary reason for screen failure
  - enrolled (defined as patients who have been assigned to a treatment) at Week 0 (Visit 2)
  - completing Period 2 (Week 12, Visit 6)
  - discontinuing the study in Period 2, by primary reason for study discontinuation
  - completing Period 3 including patients who complete the study because of GIS = 1 prior to Week 20 (Visit 10)
  - discontinuing the study in Period 3, by primary reason for study discontinuation(Analysis population: All Entered Patients)
- Number of patients:
  - completing the study treatment in Period 2
  - discontinuing the study treatment in Period 2, by primary reason for treatment discontinuation

(Analysis population: FAS Population)

- Number of patients:
  - completing the study treatment in Period 3
  - discontinuing the study treatment in Period 3, by primary reason for treatment discontinuation

(Analysis population: Maintenance Dosing Period Population)

A by-patient listing will be provided to include the following information (Analysis population: All Entered Patients):

- Patient disposition during treatment periods, including the date of enrollment at Visit 2, the date of first and last dose, the date of study completion or study discontinuation, the primary reason for study discontinuation if applicable, and the number of days in treatment periods. The number of days in treatment periods will be calculated as: date of treatment discontinuation (or treatment completion) - date of first dose in Period 2 + 1. For patients who discontinue due to lost to follow-up, the date of discontinuation captured in the *Disposition Event: Lost to Follow Up* electronic case report form (eCRF) page will be used for this calculation.

## 6.8. Patient Characteristics

### 6.8.1. Demographics and Baseline Characteristics

The following demographic variables and baseline characteristics will be summarized descriptively for patients with GPP and EP separately and total (Analysis population: FAS Population):

- Age at the time of informed consent (in years): It will be calculated using an imputed date of birth of July 1st in the year of birth collected in the *Demographics* eCRF page as follows:

$$\text{Age (years)} = \frac{\text{Date of informed consent} - \text{Imputed date of birth}}{365.25}$$

- Age group: <65 years, ≥65 years to <75 years, ≥75 years
- Gender
- Race
- Race subcategory: Japanese, other (if “No” is selected for the “Race Asian” collected in the *Demographics* eCRF page)
- Height (cm)
- Weight (kg)
- Weight category: <80 kg, ≥80 kg and <100 kg, ≥100 kg
- Body mass index (BMI) (kg/m^2): It will be calculated as follows:

$$\text{BMI (kg / m}^2\text{)} = \frac{\text{Weight (kg)}}{(\text{Height (m)})^2}$$

- Alcohol use: never, current, former
- Caffeine use: never, current, former
- Tobacco use: never, current, former
- Previous systemic therapy: never used, non-biologic only, biologic only, biologic and non-biologic.
  - Non-biologics are defined as: methotrexate, cyclosporine, retinoids, corticosteroids, fumaric acid derivatives, apremilast, other non-biologics, and psoralen and ultraviolet A (PUVA)
  - Biologics are defined as: efalizumab, ustekinumab, infliximab, etanercept, alefacept, adalimumab, golimumab, certolizumab pegol, secukinumab, brodalumab, or other biologics
- Previous non-biologic systemic therapy: never used, ever used
- Previous biologic therapy: never used, ever used
- Previous phototherapy (ultraviolet B [UVB] or PUVA): never used, ever used
- Previous IL-17 therapy (secukinumab or brodalumab): never used, ever used
- Age at GPP or EP diagnosis (in years)
- Duration since GPP or EP diagnosis (in years): It will be calculated using the date of GPP or EP diagnosis as follows:

*Duration since GPP or EP diagnosis (years)*

$$= \frac{\text{Date of informed consent} - \text{Date of GPP or EP diagnosis}}{365.25}$$

In case of partial date of GPP or EP diagnosis, the following imputation rules will be utilized:

- If both month and day are missing, impute July 1.
- If month is missing and day is not missing, impute July 1.
- If only day is missing, impute 15.
- Psoriasis vulgaris: yes, no
- Psoriatic arthritis: yes, no
- Baseline sPGA as continuous variable
- Baseline sPGA category: 0, 1, 2, 3, 4, 5
- Baseline PASI score
- Scalp psoriasis: yes, no
- Baseline PSSI score
- Baseline BSA (%)

- Baseline Itch NRS score
- Baseline DLQI total score
- Diagnosis of GPP (GPP only): acute GPP, other
- Type of GPP (GPP only): GPP with preceding psoriasis vulgaris, other: If start date of psoriasis vulgaris is prior to diagnosis date of GPP, it will be classified into GPP with preceding psoriasis vulgaris. Otherwise, it will be classified into other. If start date of psoriasis vulgaris and/or diagnosis date of GPP are missing or partial, these dates will be compared as far as possible. If there is clear evidence to suggest that the psoriasis vulgaris started prior to the diagnosis of GPP, the patient will be assumed to be GPP with preceding psoriasis vulgaris.
- Mutation of IL-36 RN (GPP only): compound heterozygous, heterozygous, homozygous, no mutation, other, unknown
- Baseline assessment of dermal symptoms total score (GPP only): It will be assessed by the score with the area of erythema (on a 0 to 3 scale), area of confluent pustules (on a 0 to 3 scale), and are of skin edema (on a 0 to 3 scale) (see table below). The total score will be calculated (range, 0 to 9).

Assessment of dermal symptoms (0 - 9 points)				
	Severe	Moderate	Mild	None
Area of erythema*	3	2	1	0
Area of erythema with pustules**	3	2	1	0
Area of edema**	3	2	1	0

\*% against body surface area (Severe:  $\geq 75\%$ , Moderate:  $< 75\% \geq 25\%$ , Mild:  $< 25\%$ )

\*\*% against body surface area (Severe:  $\geq 50\%$ , Moderate:  $< 50\% \geq 10\%$ , Mild:  $< 10\%$ )

- Baseline systemic symptoms and laboratory findings total score (GPP only): It will be assessed by the score with body temperature (on a 0 to 2 scale), leucocytes (on a 0 to -2 scale), C-reactive protein (on a 0 to 2 scale) and serum albumin (on a 0 to 2 scale) (see table below). The total score will be calculated (range, 0 to 8).

Systemic symptoms and laboratory findings (0 - 8 points)			
Score	2	1	0
Body temperature ( $^{\circ}\text{C}$ )	$\geq 38.5$	$37 \leq < 38.5$	$< 37$
Leucocytes ( $/\mu\text{L}$ )	$\geq 15,000$	$10,000 \leq < 15,000$	$< 10,000$
C-reactive protein (mg/dl)	$\geq 7.0$	$0.3 \leq < 7.0$	$< 0.3$
Serum albumin (g/dl)	$< 3.0$	$3.0 \leq < 3.8$	$\geq 3.8$

- Baseline GPP severity index total score (GPP only): It will be calculated by the sum of assessment of dermal symptoms total score and systemic symptoms and laboratory findings total score (range, 0 to 17).

- Baseline GPP severity: mild, moderate, severe (GPP only): It will be defined as mild (0 – 6 points), moderate (7 – 10 points), and severe (11 – 17 points) from GPP severity index total score.
- Baseline Columbia-Suicide Severity Rating Scale (C-SSRS) in lifetime: Category 1 – Wish to be Dead, Category 2 – Non-specific Active Suicidal Thoughts, Category 3 – Active Suicidal Ideation with Any Methods (Not Plan) without Intent to Act, Category 4 – Active Suicidal Ideation with Some Intent to Act, without Specific Plan, Category 5 – Active Suicidal Ideation with Specific Plan and Intent, Category 6 – Preparatory Acts or Behavior, Category 7 – Aborted Attempt, Category 8 – Interrupted Attempt, Category 9 – Actual Attempt (non-fatal), and Self-injurious behavior without suicidal intent.

A by-patient listing of demographic and baseline characteristics will be provided (Analysis population: FAS Population).

### **6.8.2. Historical Illness and Preexisting Conditions**

Historical illnesses and preexisting conditions will be classified using the latest version of the Medical Dictionary for Regulatory Activities (MedDRA).

Historical illness/condition is defined as the condition/event recorded on the Pre-Existing Conditions and Medical History eCRF page or on the Prespecified Medical History eCRF page with an end date prior to the date of informed consent.

Preexisting condition is defined as the condition/event recorded on the Pre-Existing Conditions and Medical History eCRF page or on the Prespecified Medical History eCRF page with a start date prior to the date of informed consent, and no end date (that is, the event is ongoing) or an end date on or after the date of informed consent. Notice if a preexisting condition worsens in severity on or after the date of informed consent, it will be recorded as an AE on Adverse Events eCRF page from the date of worsening onwards.

By-patient listings of historical illnesses and preexisting conditions will be provided, respectively (Analysis population: FAS Population).

## **6.9. Treatment Compliance**

Throughout treatment periods, enrolled patients will record information in a Study Drug Administration Log (captured in the *Exposure as Collected* eCRF page), including the date, time, and anatomical location of administration of investigational product, package number, who administered the investigational product, and the reason if the investigational product was not fully administered.

Treatment compliance for each patient will be calculated as:

$$\text{Treatment compliance (\%)} = 100 \times \frac{\text{Total number of injections administered}}{\text{Total number of injections prescribed}}$$

- For patients who complete Period 2, the number of injections prescribed (that is, expected) during Period 2 will be equal to 7 (2 injections at Week 0 and 1 injection every 2 weeks from Week 2 to Week 10).
- For patients who discontinue during Period 2, the number of injections prescribed during Period 2 can be derived from the IWRS study drug dispense dataset.
- For patients who complete Period 3, the number of injections prescribed (that is, expected) during Period 3 will be equal to 4 (1 injection every 2 weeks from Week 12 to Week 18).
- For patients who discontinue during Period 3 or who complete study treatment because of GIS = 1 (i.e., Responder) before Week 18, the number of injections prescribed during Period 3 can be derived from the IWRS study drug dispense dataset.
- The total number of injections administered will be derived using the response to the question “Was dose administered?” on the *Exposure as Collected* eCRF page.

A patient will be considered overall compliant with study treatment if he/she misses no more than 20% of the expected doses, does not miss 2 consecutive doses (all injections at an injection week are counted as 1 dose), and does not over-dose (that is, take more injections at the same time point than specified in the protocol).

The treatment compliance (continuous variable) and the number of patients that are compliant and non-compliant (categorical variable) will be summarized for patients with GPP and EP separately and total for Period 2 and for Combined Periods 2 and 3, respectively (Analysis population: FAS Population for Period 2, Maintenance Dosing Period Population for Combined Periods 2 and 3).

By-patient listings of study drug dispensed (including lot number and package number) and study treatment administration and compliance will be provided (Analysis population: FAS Population).

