3.2. Background

Ixekizumab (LY2439821, Taltz®) is a humanized immunoglobulin G subclass 4 (IgG4) monoclonal antibody (MAb) that binds with high affinity and specificity to interleukin (IL)-17A,

a proinflammatory cytokine. Ixekizumab does not bind to ligands IL-17B, IL-17C, IL-17D, IL-17E, or IL-17F.

Phase 3 clinical studies show that ixekizumab is efficacious and has an acceptable safety profile for the treatment of adult patients with moderate-to-severe Ps and for adult patients with active PsA. Ixekizumab was approved in Japan for the treatment of Ps, PsA, EP, and GPP at an initial dose of ixekizumab 160 mg followed by ixekizumab 80 mg administered Q2W from Week 2 through Week 12, and thereafter 80 mg Q4W. In August 2018, a new dosage and administration was approved in Japan to support 80mg Q2W continued dosing beyond Week 12 for patients with Ps, PsA, EP and GPP who have an inadequate response at Week 12. However, clinical studies consisting of the main data package in this new approval did not include the data from patients with EP and GPP who underwent treatment of ixekizumab 80 mg Q2W over 12 weeks. Therefore, the PMDA agreed that Eli Lilly Japan would conduct a study to evaluate the use of ixekizumab Q2W dosing beyond Week 12 in patients with EP and GPP in order to provide support for consistent dosing guidelines for the treatment of all indications (ie, Ps, PsA, EP, and GPP) with ixekizumab.

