10.3.2.4. Treatment Compliance

Treatment compliance with study drug will be summarized for patients who enter Periods 2 and 3 (Induction Dosing Period and Maintenance Dosing Period), respectively. Overall compliance with therapy is defined to be missing no more than 20% of the expected doses and not missing 2 consecutive doses, and does not overdose (that is, take more injections at the same time point than specified in the protocol).

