## 6. A Priori Statistical Methods

### 6.1. General Considerations

Statistical analysis of this study will be the responsibility of Eli Lilly Japan.

Efficacy, health outcomes and safety analyses for Period 2 will be conducted on the largest analysis set (Full Analysis Set [FAS]), defined as the set of patients with GPP and EP separately who receive at least 1 dose of study treatment in Period 2 (FAS Population). Efficacy, health outcomes and safety analyses for Combined Periods 2 and 3 will be conducted based on patients with GPP and EP separately who receive at least 1 dose of study treatment in Period 3 (Maintenance Dosing Period Population) although the protocol stated that these analyses will be conducted only for Period 3 on the Maintenance Dosing Period Population.

Baseline for efficacy, health outcomes, and safety analyses in Period 2 and Combined Periods 2 and 3 is defined as the last available value before the first dose in Period 2; in most cases, it will be the value recorded at Week 0 (Visit 2).

Change from baseline will be calculated as the value at the visit of interest minus the baseline value. If all baseline values are missing for a particular variable, then the change from baseline and the percent improvement from baseline will not be calculated.

In the analysis of adverse events for Period 2 and Combined Periods 2 and 3, all pre-existing conditions recorded at Visit 1 and any on-study adverse events recorded prior to the first dose in Period 2 will be used as baseline events.

As this is a single arm study with very small sample size, no statistical inference will be performed.

Continuous data will be summarized in terms of the mean, standard deviation (SD), minimum, maximum, median, and number of observations. The minimum and maximum will be reported to the same number of decimal places as the raw data recorded in the database. The mean and median will be reported to 1 more decimal place than the raw data recorded in the database. The SD will be reported to 2 more decimal places than the raw data recorded in the database. In general, the maximum number of decimal places reported shall be 4 for any summary statistics. Categorical data will be summarized as frequency counts.

The statistical analyses will be performed using SAS® Version 9.4 or higher.

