#### 6.13.1. Extent of Exposure

Exposure to study drug will be summarized descriptively for Period 2 and for Combined Periods 2 and 3, respectively (Analysis population: FAS Population for Period 2, Maintenance Dosing Period Population for Combined Periods 2 and 3).

A by-patient listing of exposure duration with number of active injections and total dose will be provided (Analysis population: FAS Population).

The duration of exposure will be calculated as:

$$\begin{aligned} \text{Duration of exposure (days)} \\ &= \text{Date of last visit (scheduled or unscheduled) in Treatment Period} \\ &\quad - \text{Date of first dose in Treatment Period} + 1 \end{aligned}$$

The number of patients in each of the following categories will be included in the summaries:

- $>0, \geq 7$  days,  $\geq 14$  days,  $\geq 30$  days,  $\geq 60$  days, and  $\geq 84$  days (Period 2). Note that patients may be included in more than 1 category.
- $>0$  to  $<7$  days,  $\geq 7$  to  $<14$  days,  $\geq 14$  to  $<30$  days,  $\geq 30$  to  $<60$  days,  $\geq 60$  to  $<84$  days,  $\geq 84$  days (Period 2)
- $>0, \geq 7$  days,  $\geq 14$  days,  $\geq 30$  days,  $\geq 60$  days,  $\geq 90$  days,  $\geq 120$  days, and  $\geq 140$  days (Combined Periods 2 and 3). Note that patients may be included in more than 1 category.

- >0 to <7 days, ≥7 to <14 days, ≥14 to <30 days, ≥30 to <60 days, ≥60 to <90 days, ≥90 to <120 days, ≥120 to <140 days, and ≥140 days (Combined Periods 2 and 3).

Total dose (in mg) is calculated by the number of active injections taken during the treatment period multiplied by a dose of 80 mg.

Total number of injections received will be derived using the response to the question “Was dose administered?” on the *Exposure as Collected* eCRF page and the actual dose description from IWRS study drug dispense dataset.

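### Does the SAP need a treatment compliance summary for Period 3 alone?

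*SAP*

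**What the plan says.** Protocol 10.3.2.4 states: "Treatment compliance with study drug will be summarized for patients who enter Periods 2 and 3 (Induction Dosing Period and Maintenance Dosing Period), respectively". It then defines overall compliance by three conditions: a 20% ceiling on missed doses, no two misses in a row, and no overdose.

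SAP 6.9 keeps that rule. A patient is compliant "if he/she misses no more than 20% of the expected doses, does not miss 2 consecutive doses", and does not overdose; all injections in one dosing week count as a single dose. The percentage and the yes/no flag "will be summarized for patients with GPP and EP separately and total for Period 2 and for Combined Periods 2 and 3, respectively". The first window uses the FAS and the second the Maintenance Dosing Period Population. No table covers Period 3 alone.

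SAP 6.1 announces a general move to the combined window: "Efficacy, health outcomes and safety analyses for Combined Periods 2 and 3 will be conducted based on patients with GPP and EP separately". It acknowledges that the protocol had Period 3 only for these analyses. Compliance is not among those it names.

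SAP 6.9 also says that by-patient listings of drug dispensed and of "study treatment administration and compliance will be provided", on the FAS. SAP 6.13.1 adds, on the same population: "A by-patient listing of exposure duration with number of active injections and total dose will be provided".

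**The concern.** The primary objective is the efficacy of dosing every two weeks beyond Week 12. Protocol 3.2 describes the initially approved regimen as 80 mg every two weeks "from Week 2 through Week 12, and thereafter 80 mg Q4W". Adherence to the two-week interval in Period 3 is therefore adherence to the regimen under study. A patient who took only Weeks 12 and 16 received Period 3 doses four weeks apart, yet the combined flag could still read compliant, because six fully taken Period 2 doses dilute the misses.

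The other tables do not recover the Period 3 figure. The Period 2 table is on the FAS, which includes Week 12 responders who leave the study, so one table cannot be subtracted from the other. Exposure duration runs from first dose to last visit and does not register skipped doses. If the compliance table were all a reader had, good adherence to the studied regimen could be claimed where it did not exist.

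**Working it through.** **Inputs (SAP 6.9).**
- Period 2: 2 injections at Week 0 and 1 at each of Weeks 2, 4, 6, 8 and 10. That is 2 + 5 = 7 injections in 6 doses.
- Period 3: 1 injection at each of Weeks 12, 14, 16 and 18. That is 4 injections in 4 doses.
- The SAP's own figures of 7 and 4 are reproduced. Combined: 7 + 4 = 11 injections, 6 + 4 = 10 doses.

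**Formulas.** Missed share = doses missed / doses expected. Compliance (%) = 100 × injections administered / injections prescribed. The flag is positive if the missed share is at most 20%, no two missed doses are adjacent, and there is no overdose.

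**Patterns for a Period 3 completer with no Period 2 miss and no overdose.**

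| Period 3 doses missed | Patterns | Combined missed share | Adjacent misses | Combined flag | Combined compliance | Period 3 missed share |
|---|---|---|---|---|---|---|
| Any one | 4 | 1/10 = 10% | no | compliant | 10/11 = 90.9% | 1/4 = 25% |
| 12+16, 12+18 or 14+18 | 3 | 2/10 = 20% | no | compliant | 9/11 = 81.8% | 2/4 = 50% |
| 12+14, 14+16 or 16+18 | 3 | 2/10 = 20% | yes | non-compliant | 9/11 = 81.8% | 2/4 = 50% |
| Any three | 4 | 3/10 = 30% | yes | non-compliant | 8/11 = 72.7% | 3/4 = 75% |

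Of these 14 patterns, 4 + 3 = 7 pass the combined rule and none would pass the same rule on Period 3 alone. Four of the seven differ only because one miss in four is 25%, above the 20% limit. The substantive cases are the three non-adjacent pairs. They sit exactly on the limit: one further miss in Period 2 gives 3/10 = 30% and the flag turns negative.

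**Can the combined percentage locate the misses?** No. Over Weeks 2 to 18 there are 9 single-injection doses, hence 36 pairs, of which 8 are adjacent, leaving 28. All give 9/11 = 81.8% and a compliant flag. Both misses fall in Period 2 in 6 pairs (Period 3 adherence 4/4 = 100%), one in each period in 19 (3/4 = 75%), and both in Period 3 in 3 (2/4 = 50%). These are counts of patterns, not probabilities.

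**Early responders.** SAP 6.9 says that when patients "complete study treatment because of GIS = 1 (i.e., Responder) before Week 18, the number of injections prescribed during Period 3 can be derived"; the source is the dispense dataset, so the denominator depends on data not shown. SAP 6.7 also counts early responders as completing Period 3, for which SAP 6.9 expects 4 injections. No firm figure can be given for them.

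**What depends on compliance.** The FAS and the Maintenance Dosing Period Population (SAP 6.1) require at least one dose in Period 2 or Period 3 respectively. The primary count (SAP 6.11.1) uses GIS values. Nonresponder imputation (SAP 6.3.1) is triggered by missing data or treatment discontinuation. None refers to the compliance flag or percentage.

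**The case for a change.** The strongest case for a change is that the protocol sentence ends with a word that points to one summary per period, and that SAP 6.1 declares the combined window for other analyses but not this one. The SAP keeps Period 3-only summaries elsewhere, for concomitant therapy (6.10.2) and treatment disposition (6.7). It already defines the Period 3 denominators, so the extra column needs no new data.

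Much of this stands as description. By-period summaries are the more natural reading, and the combined flag is lenient about Period 3. Three things limit it. The protocol sentence speaks of patients who enter each period and then defines overall compliance. SAP 6.9 reports exactly those two patient groups, so its reading is permissible. Protocol 10.3.1 sends changes to analysis methods that are not a principal feature to the clinical study report, with justification; it does not require them in SAP 6.1. Finally, a Period 3 flag would mean only that some dose was missed. That is a reasonable ground for preferring the larger denominator, and it leaves the percentage as the only useful addition.

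Conduct also counts against the worst case. All four Period 3 doses fall on scheduled visits with compliance review (Protocol Section 2), and a missed dose is to be given within 4 days (Protocol 7.2.1). The 20% pattern needs two separate unrecovered misses at those visits.

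**Conclusion.** No change to the plan is needed, because none would alter a result or a conclusion. The combined flag can call a patient compliant with half the Period 3 doses missed, but for a completer this happens in three boundary patterns only. Compliance enters no population, imputation or test in a study that plans no inference, so the primary count is unaffected.

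With 12 patients planned, the administration and compliance listings show at patient level what the table merges. This assumes that they present injections by date, as the administration log collects them. The figures above also assume no overdose and all four Period 3 doses expected. Enrolment may be increased, but nothing in the plan suggests a size at which listings become unreadable. A Period 3 percentage would be a convenience, and a sentence in the clinical study report is enough to describe the difference from Protocol 10.3.2.4.
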